The objective of the proposed research is to evaluate a promising strategy for CPAP level selection: a physiologic approach minimizing V/Q mismatch and measured non-invasively at the infants bedside. We propose the following specific Aims and hypotheses in support of this objective: Aim 1 (primary): measure the responsiveness of V/Q mismatch to a strategy of individualized CPAP level selection. We hypothesize that V/Q mismatch will, on average, improve by 10% of baseline V/Q mismatch at the best identified CPAP level. Aim 2: describe the distribution of best CPAP levels as identified by our strategy. Best CPAP levels will be described as both absolute values and relative to baseline (+2 cm H₂O, -1 cm H₂O, etc.). For this exploratory aim, we hypothesize that a best CPAP will be identified above the baseline in greater than 50% but less than 80% of subjects. Demonstrating that most but not all infants benefit from higher pressures will highlight the importance of individualized CPAP level selection in premature infants.

Primary outcome variable(s)

Primary outcome measure: V/Q mismatch. This parameter will be calculated by computer software on the basis of the curvilinear characteristics generated by a best-fit curve connecting the FiO₂/SpO₂ pairs obtained during the study protocol. With lower V/Q and greater mismatch, the curve is progressively displaced to the right relative to a curve corresponding to an ideal reference lung (interrupted, left-most curve in Figure 2, see attached documents). The V/Q ratio is displayed on the software output after the FiO₂/SpO₂ pairs are input. Additionally, this parameter is also displayed as the degree of right-shift relative to the ideal reference lung (greater values indicate more mismatch), providing a positive continuous number with units of % FiO₂ as an alternative measure to the ratio value with greater ease of use. This will be measured twice at baseline without a change in CPAP level and then following each CPAP level change. The primary outcome measure is the responsiveness of V/Q mismatch to a strategy of individualized CPAP level selection, measured as the improvement in V/Q mismatch between the second baseline level and best identified CPAP level for each subject (see Figure 3 in attached documents.) For infants not responding to either +1 or -1 cm H₂O CPAP level changes, baseline CPAP will be defined as best, with zero assigned as the improvement in V/Q mismatch.

Secondary outcome variable(s)

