Secondary outcome: best CPAP level. Our second Aim is to describe the distribution of best CPAP levels as identified by our strategy. We hypothesize that best CPAP will vary between infants, resulting in a distribution of values. Best CPAP level will be identified as the lowest CPAP level associated with an improvement greater than 5% in V/Q mismatch relative to the preceding CPAP level, as described in the study protocol. This will be "measured" once at the conclusion of the study protocol. Excessive

airway pressures can result in lung over-distension and can plausibly result in adverse cardiopulmonary interactions through transmission of positive pressure to the heart and intra-thoracic vessels (however, this has not been observed in any modern CPAP level studies performed in premature infants, see Table 1). We will measure the impact of CPAP level changes on the following readily available clinical cardiovascular parameters during the study protocol: Mean arterial blood pressure will be measured with a neonatal blood pressure cuff used for routine clinical care and placed on an upper extremity or through pressure transduction of an indwelling arterial catheter, when present (uncommon in our subject population), with units of mm Hg. This outcome will be recorded at the end of each baseline and CPAP level period by the research team. Heart rate will be measured and displayed by the study pulse oximeter, with units of beat per minute. This outcome will be recorded at the end of each baseline and CPAP level period by the research team. Additional data to be collected will include: i) demographic data; (gestational age, birth weight, gender, race, etc.) ii) baseline variables (receipt of antenatal steroids, Apgar scores, age in hours and FiO₂ at intervention, most recent hemoglobin level, CPAP pressure source and interface, etc.) and iii) important or pertinent in-hospital neonatal outcomes (survival to discharge, BPD, brain injury by ultrasound, patent ductus arteriosus, necrotizing enterocolitis, retinopathy of prematurity, duration of: MV days, CPAP and supplemental oxygen, etc). This data will be used to explore associations between these variables and both a) baseline V/Q mismatch and b) the responsiveness of this parameter to CPAP level changes, with a goal of supporting hypothesis generation for subsequent research

Background

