
No active consideration of endotracheal intubation; as determined by the clinical Attending of record. 2. No hemodynamic instability, defined as a baseline heart rate less than 100 beats per minute (bpm) or greater than 180 bpm; or a mean arterial blood pressure of less than 30 millimeters of mercury (mm Hg). 3. No supplemental FiO₂ requirement greater than 0.45. 4. No capillary/arterial partial pressure of carbon dioxide greater than 65 mm Hg on last blood gas analysis, unless performed more than 6 hours prior. 5. No more than 6 apnea/bradycardia/desaturation events requiring tactile stimulation or more than 1 requiring positive pressure bag ventilation in the preceding 6 hours. Initiation of the study protocol will be deferred until these criteria are met. Figure 3 depicts the study protocol as applied in one hypothetical subject. Of note, the protocol will vary between subjects with respect to the direction and extent of CPAP level changes, as determined by the absence or presence of a response at each step-wise CPAP level change. This is described in detail below. Subjects will undergo the study interventions in their routine clinical environment. The clinically selected CPAP interface and pressure source will be maintained. A study pulse-oximeter, with low motion artifact and a short averaging time, will be placed on a post-ductal limb and used for SpO₂ measurements. V/Q will first be measured on two separate occasions 30 minutes apart at baseline CPAP, set by the clinical team. The repeat baseline measures will allow an estimate of the stability of V/Q as a function of time (further discussed in Confounding under Analysis Plan). To measure V/Q mismatch, gradual changes in delivered FiO₂, followed by SpO₂ measurement, will be applied to obtain three FiO₂/SpO₂ pairs, one each for SpO₂ values in the ranges of 85-87%, 89-91% and 93-95%. To obtain each SpO₂ range, FiO₂ will be titrated gradually until SpO₂ falls within the desired values. After 60 seconds of stabilization at the identified FiO₂ value, SpO₂ will be recorded every 30 seconds for 2 minutes if an adequate signal waveform is present, providing up to four SpO₂ values. These values will be averaged to calculate the SpO₂ value used for the FiO₂/SpO₂ pair, acknowledging the inherent instability of pulse-oximeter values over time in premature infants. A computer software program will immediately calculate V/Q from the identified FiO₂/SpO₂ pairs at the bedside. Next, CPAP will be increased by +1 cm H₂O. A period of 15 minutes will elapse to allow equilibration of lung volumes in response to the CPAP level change (24). V/Q calculations as described above will be repeated. A positive response will be defined as an improvement in V/Q at the new pressure level of 5% relative to the preceding CPAP level. Responders will undergo subsequent stepwise +1 cm H₂O increases up to +3 cm H₂O from baseline or 8 cm H₂O; whichever is less. Infants not responding to the initial +1 cm H₂O increase will return to baseline CPAP for 15 minutes and then be assessed at -1 cm H₂O from baseline. Infants responding at this lower CPAP level will undergo an additional decrease to -2 cm H₂O from baseline or 3 cm H₂O; whichever is greater. The allowed range of -2 to +3 cm H₂O reflects our institutional practice of typically setting a baseline CPAP level of 5 or 6 cm H₂O and a CPAP pressure range of 4 to 8 cm H₂O used in international trials. Best CPAP will be defined as the lowest (and last) CPAP level at which a positive response, as defined above, is measured. The baseline CPAP level will be defined as best for those infants not responding to either +1 or -1 cm H₂O CPAP level changes, with a corresponding V/Q improvement of zero. Upon completion of the study protocol, infants will be returned to their baseline CPAP level. The study protocol will typically require between 60 and 120 minutes. Throughout the study, a set of pre-defined stopping criteria will be monitored to ensure subject tolerance of the study procedures. These criteria are designed to be conservative safety measures and will result in study termination and provision of supportive care, as needed. Patient Safety Considerations: Extensive patient safety considerations minimizing the risks associated with implementation of this phase II design research protocol have been incorporated: 1. Many of the key eligibility (inclusions and exclusion) criteria reflect the deliberate selection of a premature infant population that is inherently less vulnerable and at lower risk of common morbidities of prematurity and less likely to suffer any adverse outcomes from implementation of the study procedures. a) I1. Corrected gestational age 27-35 weeks (GA): this selects a study population in which respiratory distress syndrome is common and CPAP is frequently used, while avoiding less mature infants with a CGA less than 27 weeks who are more prone to physiologic instability. We exclude this population in consideration of safety for this phase II study despite a high risk of CPAP failure and a potential for benefit from our long-term research goals of establishing methods to prevent CPAP failure. b) I2. Chronologic age of greater than 24 hours. This avoids study of infants during the first 24 hours of life when they may be more prone to physiologic instability. c) I3. On continuous CPAP support for greater than 24 hours. This prioritizes safety by restricting study to subjects demonstrating stability on CPAP therapy, in contrast to infants newly transitioned to CPAP without a period of demonstrated tolerance. d) I4. Supplemental oxygen requirement, with a fraction of inspired oxygen (FiO₂) 0.25 for at least 2 consecutive hours. This ensures that CPAP level changes are only performed in infants requiring supplemental oxygenation, suggesting V/Q mismatch and/or shunt from atelectasis. These subjects would plausibly benefit from carefully monitored changes in continuous distending airway pressure to counteract the pathophysiology resulting in the oxygen need. This criteria avoids CPAP

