
The following documents are currently attached to this item:

There are no documents attached for this item.

Deception

Does your project use deception?

No

International Research

Are you conducting research outside of the United States?

No

Analysis Plan

Results will be summarized using basic descriptive statistics. For Aim 1, a paired t-test for parametric results or a Wilcoxon signed-rank test for non-parametric results will be used to test our hypothesis that V/Q mismatch will improve at best CPAP level compared to baseline. For Aim 2, we will calculate the proportion of subjects in which best CPAP level is identified above the baseline pressure level to assess our hypothesis that this occurs in greater than 50% but less than 80% of subjects. Further, best CPAP for the cohort will be summarized as mean and standard deviation (if parametric) or median and interquartile range (if non-parametric). No formal statistical testing of significance will be performed for this second descriptive Aim. The change in V/Q over the two baseline periods, as well as the change in heart rate and blood pressure between baseline and best CPAP levels will be tested using the statistical approach as Aim 1. We predict the null hypothesis of no significant difference for these comparisons. Should a significant change in V/Q be identified between baseline periods, we will perform an additional analysis comparing the change in V/Q between baseline periods to the change in V/Q between baseline and best CPAP level to account for the independent impact of time on V/Q

mismatch. Confounding: key elements of our study design limit confounding for Aim 1, to measure the responsiveness of V/Q mismatch to a strategy of individualized CPAP level selection. The use of a pre-post within-patient analysis limits confounding from variation in between-patient characteristics. A remaining important source of confounding is the possibility that V/Q simply improves over time irrespective of CPAP pressure changes. We account for this by measuring V/Q on two separate occasions 30 minutes apart at baseline CPAP in the study protocol, facilitating an assessment of the stability of V/Q over time.

The following documents are currently attached to this item:

There are no documents attached for this item.

Data confidentiality

- Paper-based records will be kept in a secure location and only be accessible to personnel involved in the study.**

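### The only named heart-rate and blood-pressure test compares baseline with best CPAP, so readings at raised levels without a V/Q response are recorded but fall outside it

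*Combined protocol and SAP*

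**What the plan says.** All references are to the combined protocol and SAP.

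- **Purpose** (Secondary outcome variable(s)): "We will measure the impact of CPAP level changes on the following readily available clinical cardiovascular parameters during the study protocol". The reason given is that excessive "airway pressures can result in lung over-distension and can plausibly result in adverse cardiopulmonary interactions". The same sentence adds that this has not been seen in modern CPAP level studies in premature infants.
- **Recording** (same section), for mean arterial pressure and again for heart rate: "This outcome will be recorded at the end of each baseline and CPAP level period by the research team". Periods at levels that fail to produce a response are included.
- **Test** (Analysis Plan): "the change in heart rate and blood pressure between baseline and best CPAP levels will be tested using the statistical approach as Aim 1". That approach is a paired t-test or a Wilcoxon signed-rank test. The authors expect the null hypothesis to stand.
- **Best CPAP** (Procedures): "Best CPAP will be defined as the lowest (and last) CPAP level at which a positive response, as defined above, is measured". If neither +1 nor -1 cm H₂O gives a response, baseline is best and the V/Q improvement is set to zero.
- **Reference reading for Aim 1** (Primary outcome variable(s)): "measured as the improvement in V/Q mismatch between the second baseline level and best identified CPAP level for each subject".
- **Aim 2 hypothesis** (Overall objectives): "a best CPAP will be identified above the baseline in greater than 50% but less than 80% of subjects".

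**The concern.** The stated question is what changing the CPAP level does to blood pressure and heart rate, and the stated worry is too much pressure. The named test selects its level by a different variable, the V/Q response. Every infant who can be raised is tried at +1 first, but that reading enters the test only if V/Q mismatch improved. The readings left out are thus raised-pressure readings, which bear directly on the stated worry.

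What is at stake is interpretation. A non-significant baseline-to-best comparison describes the levels that the strategy selects. It does not describe raised CPAP at the steps that failed, because it contains no observation from them.

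**Working it through.** **1. The plan's own figure.** The only power statement is for Aim 1: 20 infants, mean change 10%, SD of the difference 15%, two-sided alpha 0.05. The standardised effect is 10/15 = 0.667 and the noncentrality is 0.667 × √20 = 2.98 on 19 degrees of freedom. Power is 80.7%, so the stated 80% reproduces. It does not carry over to this point, because the documents give no SD for heart rate or blood pressure.

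**2. What each path puts into the test** (Procedures set against the Analysis Plan):

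| Path | Best CPAP | Raised-pressure reading in the test | Raised-pressure reading left out |
|---|---|---|---|
| Responds at every step up to the limit | Above baseline | Yes | No failed step to leave out |
| Responds, then fails a higher step | Above baseline | Yes, at the last responding level | The highest level tested |
| Fails +1, responds at -1 | Below baseline | None | +1 |
| Fails +1 and -1 | Baseline | None | +1 |

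For the last row the plan assigns zero to the V/Q improvement. It gives no rule for heart rate or blood pressure.

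**3. How many infants.** More than 50% of 20 is more than 10, and less than 80% is fewer than 16. So 11 to 15 infants have best CPAP above baseline, and 20 - 15 = 5 to 20 - 11 = 9 do not. As shares, 5/20 = 25% and 9/20 = 45%. These are the last two rows of the table.

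The count assumes that each of these infants completes the +1 step. Procedures cap the pressure at 8 cm H₂O, so an infant with a baseline of 8 has no up-step to lose. Such infants should be few, since the institution is described as "typically setting a baseline CPAP level of 5 or 6 cm" H₂O.

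The number in the second row cannot be derived, because the documents give no chance of response at the second or third step.

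**4. What the stopping criteria cover.** For mean arterial pressure, an infant is stopped by a fall of more than 20%, or by a fall of more than 10% that also goes below 30 mm Hg.

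- Baseline of 37.5 mm Hg or more: 0.8 × 37.5 = 30, so only a fall of more than 20% stops the infant.
- Baseline of 30 to 33.3 mm Hg: 0.9 × 33.3 = 30, so any fall of more than 10% stops the infant.
- In between, the infant is stopped on going below 30 mm Hg, a fall of between 10% and 20%.

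These are thresholds for one infant. They apply at failed steps too, but they do not produce a mean change, and a moderate fall from a higher baseline leaves no trace in the early-termination count.

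**5. Precision of a failed-step summary.** The 95% CI half-width is t(0.975, n-1)/√n in units of the SD of the change. For n = 5 it is 2.776/2.236 = 1.24 SD. For n = 9 it is 2.306/3 = 0.77 SD.

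**The case against.** The strongest reply is that the plan gives tolerance to other instruments. Procedures say the stopping criteria are there to ensure that subjects tolerate the study. They track heart rate and mean arterial pressure at every level. Data and Safety Monitoring adds an early-termination count with an expectation below 20%, and a committee review after 7 and 14 subjects. The Analysis Plan promises descriptive statistics in general, and nothing there forbids a by-level table. The plan regards the effect as unlikely: Potential Study Risks reports earlier studies up to 9 cm H₂O without reported concerns for harm. Baseline-to-best is also a coherent contrast for a strategy of CPAP selection, and 11 to 15 infants do supply raised-pressure readings to it.

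Most of this stands. It limits the weight of the point but does not close the gap. Individual thresholds do not estimate a mean change, and the descriptive-statistics sentence names neither the cardiovascular variables nor any CPAP level.

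Three stronger readings that a reader might infer are not supported:

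- *That the plan would take a non-significant result as proof that raised CPAP is tolerated.* It predicts no difference but nowhere draws that conclusion.
- *That failed up-steps are where cardiovascular harm is expected.* Patient Safety Considerations link non-response to a raise with adequate lung volume at baseline. They do not say that over-distension or a circulatory effect occurs at a failed +1 step.
- *That a missed effect, or the share of infants losing their highest-pressure reading, can be quantified.* Either would need a cardiovascular SD, an effect size or step-by-step response chances, and the documents give none of these.

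**Conclusion.** The point holds as a gap between a stated secondary objective and its named analysis. The objective concerns CPAP level changes, while the test covers only the selected level. By the plan's own Aim 2 range, 5 to 9 of 20 infants (25-45%) would give the test no raised-pressure reading. An unknown further number would lose the reading at their highest pressure. The count rests on 20 evaluated infants, on the Aim 2 hypothesis being right, and on completion of the first +1 step.

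The primary analysis and its sample size are unaffected. The measures are secondary, without a power claim, and partly protected by the stopping criteria. The change is worth making because the data are already to be collected, not because the documents point to a likely harm.

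**What to change.** - Keep baseline-to-best as the strategy contrast for heart rate and mean arterial pressure. State that it uses the second baseline, as in Aim 1.
- Add a secondary descriptive summary of the change from the second baseline to each raised level tested, by step size (+1, +2, +3) and by whether the step succeeded or failed, and to the highest level tested in each infant. Give the mean change, its 95% CI and the worst individual change.
- List separately, with the reason, infants stopped mid-period for whom no reading was recorded.
- Interpret the results by which changes the interval excludes, and not by non-significance.

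The cost is a little more analysis, with no new scheduled measurements and no change to clinical management. The limits should be stated with the results. A failed-step estimate in 5 to 9 infants is imprecise (half-width 1.24 to 0.77 SD). The highest-level contrast mixes step sizes, and only responders reach the higher steps.

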This study will enroll up to 30 patients in order to evaluate 20 subjects. Infants will be screened for eligibility by the research team using routinely available clinical data from the electronic health record. Informed consent will be obtained from parents or guardians approached within the HUP ICN, PAH ICN, or the CHOP N/IICU during the eligibility window as described below. The diagram depicted in Figure 4 summarizes expected enrollment in consideration of our eligibility criteria and additional barriers to successful recruitment and study application. This estimate suggests a 10-month window of active enrollment will be required to meet our recruitment goals, making our one-year recruitment goal feasible. Aim 1 guides sample size considerations. Using a paired test of correlated means, a sample size of 20 evaluated infants will provide 80% power to detect an overall average percent change of 10% from baseline, assuming a 15% standard deviation of the difference and a two-sided alpha level of 0.05.

Key inclusion criteria

I1. 27-35 weeks corrected gestational age (CGA) by best obstetric estimate, determined by the clinical obstetric team during antepartum admission and chronologic age, measured from date of birth I2. Chronologic age greater than 24 hours, measured from time of birth. I3. On CPAP support between 4-8 cm H₂O for greater than 24 hours, as document on the bedside infant flow sheet. I4. Supplemental oxygen requirement, with a fraction of inspired oxygen (FiO₂) 0.25 for at least 2 consecutive hours, as documented on the bedside infant flow sheet. (Infants without an oxygenation requirement are unlikely to have significant V/Q mismatch. Further, FiO₂ titrations (see Procedures) are required to apply the non-invasive technique, resulting in limited applicability to infants with little or no supplemental oxygen requirement).

Key exclusion criteria

E1. Congenital anomalies, as determined by the clinical supervising physician. E2. Current or prior air leak syndrome, as determined by the clinical supervising physician.

Vulnerable Populations

Children Form

Pregnant women (if the study procedures may affect the condition of the pregnant woman or fetus) Form

Fetuses and/or Neonates Form

Prisoners Form

Other

None of the above populations are included in the research study

The following documents are currently attached to this item:

There are no documents attached for this item.

Populations vulnerable to undue influence or coercion

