
level changes in infants on CPAP but not requiring supplemental oxygen as they are less likely to benefit from changes in pressure level. e) E2. Exclusion of infants with current or prior air leak syndrome. This avoids study in infants with suggestion of a pathophysiology that could worsen with increased CPAP levels. 2. To further avoid study in infants with physiologic instability, the following criteria will be met prior to initiation of the study procedures; with deferral of the study until they are met: a. No active consideration of endotracheal intubation; as determined by the clinical Attending of record. b. No hemodynamic instability, defined as a baseline heart rate less than 100 beats per minute (bpm) or greater than 180 bpm; or a mean arterial blood pressure of less than 30 millimeters of mercury (mm Hg). c. No supplemental FiO₂ requirement greater than 0.45. d. No capillary/arterial partial pressure of carbon dioxide greater than 65 mm Hg on last blood gas analysis, unless performed more than 6 hours prior. e. No more than 6 apnea/bradycardia/desaturation events requiring tactile stimulation or more than 1 requiring positive pressure bag ventilation in the preceding 6 hours. 3. Stepwise changes in CPAP level, with assessment after each CPAP level change and restriction of further pressure changes to instances in which there is a response suggestive of improving physiology - defined as greater than a 5% improvement of baseline V/Q mismatch. Infants who are at inadequate lung volumes at baseline CPAP are likely to show benefit with higher pressure levels, while infants with adequate lung volumes at baseline CPAP are unlikely to show any physiologic benefit at higher pressure levels. Similarly, infants with over distended lung volumes at baseline may benefit from lower pressure levels, while infants with adequate lung volumes at baseline CPAP are unlikely to show benefit with lower pressure levels. This key element of study procedures will protect against the risk of over-distension or loss of lung volumes secondary to the study procedures. 4. Stopping Criteria. The following "stopping criteria" will be monitored in each subject throughout the study procedures and will result in study termination, provision of supportive care and a return to baseline settings when appropriate: a) a drop in mean arterial pressure to a mmHg value less than 30 mm Hg and in excess of 10% from the baseline value, or in excess of 20% of baseline value. b) an increase in heart rate to greater than 190 bpm and in excess of 10% from the baseline value or in excess of 20% of the baseline value. c) with an adequate pulse waveform, a sustained drop in SpO₂ to less than 80% for greater than one minute or a drop in SpO₂, to less than 75% for greater than 30 seconds or less than 45% for any duration of time. d) a two-fold increase in the hourly frequency of cardiorespiratory events (apnea/ bradycardia/desaturation) relative to the average frequency in the four hours prior to study initiation. For infant without any events in the four hours prior to study initiation, greater than one event per hour will be used as a threshold. Further, any single event requiring bag- mask positive pressure ventilation will lead to study termination.

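### Heart rate and blood pressure get only a difference test with the null predicted, so in about 20 infants a non-significant p-value would not by itself show absence of a cardiovascular effect

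*Combined protocol and SAP*

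**What the plan says.** Under Secondary outcome variable(s), the protocol raises the possibility that excessive airway pressure harms heart-lung interaction. It answers with heart rate and MAP: "We will measure the impact of CPAP level changes on the following readily available clinical cardiovascular parameters during the study protocol". Both are recorded at the end of every baseline and CPAP level period. The Design section names safety monitoring as one goal of a phase II trial.

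The Analysis Plan then provides that "the change in heart rate and blood pressure between baseline and best CPAP levels will be tested using the statistical approach as Aim 1". For Aim 1, "a paired t-test for parametric results or a Wilcoxon signed-rank test for non-parametric results will be used". The prediction follows: "We predict the null hypothesis of no significant difference for these comparisons". That sentence also covers the change in V/Q between the two baseline periods. The only other reporting commitment is general: "Results will be summarized using basic descriptive statistics".

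The Accrual section bases the sample size on Aim 1 (V/Q). Its inputs for spread and error rate are worded "assuming a 15% standard deviation of the difference and a two-sided alpha level of 0.05", and the claim built on them is that "a sample size of 20 evaluated infants will provide 80% power to detect an overall average percent change of 10% from baseline". It gives no SD, effect size or margin for heart rate or MAP.

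Safety is also handled elsewhere. The stopping criteria under Procedures include, for an individual infant, "a drop in mean arterial pressure to a mmHg value less than 30 mm Hg and in excess of 10% from the baseline value", or a fall of more than 20% alone, with parallel limits for a rise in heart rate. Data and Safety Monitoring adds committee review after 7 and 14 enrolled subjects, an expectation that fewer than 20% of enrolled subjects stop early, and monitoring after the procedure.

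**The concern.** A test for a difference can give evidence of a change. Failing to reject does not give evidence of no change unless precision is also shown. Here the null is the predicted result and a p-value is the only inferential output, so the noisier the readings, the more easily the prediction is met. A reader given only a non-significant p-value could not tell a well-estimated change near zero from an imprecise estimate compatible with a material average fall in MAP or rise in heart rate. These two measures are the trial's named response to its own cardiopulmonary concern, in a vulnerable population, so the report should say how large an average effect the data leave open.

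**Working it through.** **Inputs from the documents.** n = 20 evaluated infants, two-sided alpha 0.05, paired analysis; for V/Q only, mean change 10% and SD of the difference 15% (Accrual).

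**Assumed, because the documents give no figure.** SD of the change in heart rate or MAP: 5% to 25% of baseline, or 4 to 8 mm Hg for MAP. Baseline MAP 35 mm Hg. Group-mean margins of 5% and 10%, for illustration only.

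**1. The plan's own power.** Noncentrality = (10/15) × √20 = 2.98 on 19 degrees of freedom. The two-sided paired t-test has power 80.7%, which matches the stated 80%. The figure is sound, but it is about V/Q.

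**2. What the same test can detect for heart rate or MAP.** Solving the power equation for 80% at n = 20 gives a mean change of 0.66 SD. The 95% interval half-width is t(0.975, 19) × SD/√20 = 2.093/4.472 × SD = 0.47 SD.

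**3. How often a real mean change would be non-significant.**

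| SD of change | True 5% change missed | True 10% change missed | 95% half-width |
|---|---|---|---|
| 5% | 1% | <1% | 2.3% |
| 10% | 44% | 1% | 4.7% |
| 15% | 71% | 19% | 7.0% |
| 20% | 81% | 44% | 9.4% |
| 25% | 86% | 60% | 11.7% |

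**4. Illustration in mm Hg (MAP).** The half-width is 1.9 mm Hg at SD 4 and 3.7 mm Hg at SD 8.
- SD 8, observed mean fall 3: t = 3/(8/√20) = 1.68, p = 0.11, 95% interval −6.7 to +0.7. The lower end is 6.7/35 = 19% of the assumed baseline.
- SD 4, observed mean fall 1.8: t = 1.8/(4/√20) = 2.01, p = 0.059, 95% interval −3.7 to +0.1. The lower end is 3.67/35 = 10.5%.

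Both results would be reported as no significant difference.

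**5. Could 20 infants exclude a meaningful mean change?** Take the true change as zero and ask how often the whole 95% interval falls inside a margin. For a 10% margin: 98% of the time at SD 10%, 62% at SD 15%, 18% at SD 20%. For a 5% margin: 98% at SD 5%, 18% at SD 10%. The chance reaches 80% when the SD is at most 13.1% (10% margin) or 6.5% (5% margin). With a 90% interval, the usual equivalence-test convention, those limits are 14.7% and 7.4%. So the answer can be yes or no, depending on the SD.

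**6. The contrast tested.** Infants who respond to neither +1 nor −1 cm H₂O have baseline as best CPAP, so they contribute no pressure contrast. The plan assigns them zero for V/Q and is silent for heart rate and MAP. If they were entered as zero (an assumption), simulated power for a 10% change at SD 15% falls from 81% to 70% with 20% such infants, and to 45% with 50%. Aim 2 expects best CPAP above baseline in more than 50% but fewer than 80% of infants, so the remainder would be at or below it. Pooling pressure rises with pressure falls lets opposite effects offset each other. Readings at a level that produced no V/Q response do not enter the comparison, although they are recorded.

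**The case against.** The strongest reply is that nothing in the plan turns on this p-value. No success criterion, decision or safety conclusion is tied to it; the text states a prediction about secondary outcomes. Safety rests on stopping criteria for each infant, committee review, the early-termination proportion and follow-up. This stands. A reader might infer that a non-significant result will be taken as proof of cardiovascular safety, but the documents state no such rule. What the reply does not supply is an estimate of the average effect, since stopping rules and termination counts do not give one.

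A second reply is that a large effect would show in the stopping data. If changes are roughly normal, a mean fall of 3 with SD 8 mm Hg and baseline 35 puts the 20% threshold (7 mm Hg) at z = (7 − 3)/8 = 0.5, so about 31% of infants would pass it, against the expected fewer than 20% stopping early. That is fair for the noisy example. It is weaker at SD 4 with a mean fall of 1.8: z = (7 − 1.8)/4 = 1.3, or about 10%, which would not stand out.

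A third reply is that the 10% and 20% figures in the stopping criteria cannot serve as a ready-made margin. This also stands. The 10% counts only together with MAP below 30 mm Hg or heart rate above 190 bpm; only 20% stands alone; for heart rate only increases count; and all are limits for one infant, not for a group mean.

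**Conclusion.** The point holds in a limited form. With a difference test only, the null as the predicted result, and a sample sized on V/Q, non-significance alone would not show absence of a cardiovascular effect. In SD units the size needs no outside figure beyond approximate normality: 0.66 SD detectable at 80% power, and a 95% half-width of 0.47 SD. Anything in mm Hg or percent rests on the assumed SDs and baseline above.

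A reader might go further and conclude that 20 infants cannot support any statement about cardiovascular effect. The documents do not establish that. With an SD up to about 13% to 15% of baseline, 20 infants would have about 80% power to exclude a 10% mean change if the true change were zero. The gap is the missing interval and margin, not the sample size as such. Severity is modest, because these are secondary outcomes in a small physiologic study with separate safety oversight.

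**What to change.** In the Analysis Plan, for heart rate and MAP:

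- Replace the predicted null with the mean (or median) change and its 95% confidence interval, in native units and as percent of baseline.
- List or plot each infant's change, using the readings already recorded at every CPAP level. State how infants whose best CPAP equals baseline are handled.
- Describe the comparison as exploratory.
- Allow a statement of no meaningful change only if the whole interval lies within a group-mean margin that the investigators specify in advance and justify. Otherwise report the result as inconclusive. The per-infant stopping thresholds should not be carried over as that margin without their own justification.

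The cost is analysis wording and the effort of justifying a margin. No infants, measurements or procedures are added. The downside is that a noisy result must be reported as inconclusive.
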